4. AMENDMENTS AND UPDATES

None (original protocol).

5. MILESTONES

Estimated Milestone	Estimated Date		
Final protocol submitted to the PRAC:	October 2013		
Protocol approved with PRAC comments received	January 2014		
Sign Off of the updated protocol	May 2014		
Submission to the EU-PAS register	June 2014		
Start of data collection (first patient in)	September 2014		
End of data collection (last patient out)	April- May 2015		
Study progress reports	As requested		
Final study report	October 2015		

6. RATIONALE AND BACKGROUND

6.1. Background

Chronic primary immune thrombocytopenia (ITP)

Chronic primary ITP is an acquired immune mediated disorder characterized by isolated thrombocytopenia, defined as a peripheral blood platelet count less than 100×10^9 /L, the absence of any underlying cause, and lasting for more than 12 months (Rodeghiero, 2009).

In Europe, adult ITP has an incidence range of 1.6 to 3.9 cases per 100,000 person-years with increasing incidence with older age. Estimates of prevalence range widely from 9.5 to as high as 189.3 per 100,000 population; prevalence is similar amongst men and women, except in the mid-adult years (i.e., 30-60 years of age), when the disease is more prevalent in women (Deane, 2010).

Diagnosis of ITP is one of exclusion, when the history, physical examination, complete blood count and examination of peripheral blood smear do not suggest other etiology for the thrombocytopenia. Physical examination is typically normal apart from signs of bleeding and the peripheral blood count reveals isolated thrombocytopenia and normal red cell and white cell indices. If significant bleeding occurs there may be anemia proportional to the degree of bleeding with possible iron deficiency. Peripheral blood smear typically shows platelets normal to large in size with no abnormalities seen in red and white cell morphology. Bone marrow examination is currently not routinely conducted in patients with typical ITP presentations, but reserved for selected cases such as those with an atypical presentation.

Guidelines and consensus documents generally recommend clinical intervention in adults when platelet counts are $<30 \times 10^9/L$ (Provan, 2009); treatment is rarely indicated for patients with platelets $>30 \times 10^9/L$ unless they are undergoing a procedure likely to induce blood loss including surgery, dental extraction or childbirth (British Committee for Standards in Haematology General Haematology Task Force, 2003). Thrombopoietic agents have been extensively studied in ITP, and are increasingly used in patients with thrombocytopenia related to other chronic diseases.

Chronic Hepatitis C Virus (HCV) Infection

The global prevalence of chronic HCV infection is 130–170 million with an annual incidence of three to four million (WHO, 2013). A majority of HCV infected patients develop chronic liver disease making it a leading cause of cirrhosis and hepatocellular carcinoma worldwide.

The goal of medical therapy in HCV is to achieve sustained virologic response (SVR) defined as prolonged clearance of HCV RNA. Until recently, treatment of HCV consisted of combination therapy of a weekly injection of a pegylated interferon and oral ribavirin.

There are six types of HCV genotype; the viral genotype is integral in determining appropriate treatment regimens, with genotype 1 being particularly difficult to treat successfully. Less than 50% of genotype 1 patients achieve a sustained viral response (SVR) with standard peginterferon-ribavirin. Boceprevir and telaprevir were the first HCV protease inhibitors to be approved for the treatment of HCV genotype 1. These drugs must be used in combination with pegylated interferon (triple therapy) plus ribavirin to maximize efficacy and prevent the emergence of resistance-associated variants (Ferenci, 2011).

Treatment related toxicity is the primary limiting factor in HCV interferon-based therapy with significant side effects necessitating dose reductions in almost half of treated patients and discontinuation in nearly a third of all patients (National Institutes of Health Consensus, 2002). Thrombocytopenia is a dose and/or therapy-limiting side effect in patients with HCV receiving interferon-based therapies. Thrombocytopenia may be a result of antiviral treatment, but may also develop as a complication of chronic HCV infection, unrelated to antiviral treatment.

In patients with HCV, thrombocytopenia occurs most commonly in those with advanced liver disease and cirrhosis. In such patients, thrombocytopenia render patients ineligible for antiviral treatment and requiring dose reductions or discontinuation and may also prevent patients from having liver biopsies and other invasive procedures, thereby hampering a physician's ability to stage and monitor the patient's liver condition. Until recently, the treatment options for thrombocytopenia in HCV affected patients were limited to intravenous immunoglobulins, corticosteroids, platelet transfusions, and cytokines, and in severe cases, splenectomy.

REVOLADE (eltrombopag)

REVOLADE (eltrombopag; GlaxoSmithKline, Research Triangle Park, NC, USA) is an oral, non-peptide, thrombopoietin receptor (TPO-R) agonist that interacts with the TPO-R and induces differentiation of hematopoietic stem and progenitor cells to megakaryocytes.

REVOLADE received marketing authorization from the European Medicines Agency (EMA) in March 2010 for the treatment of adult splenectomised chronic ITP patients who are refractory to other treatments (e.g., corticosteroids, immunoglobulins). As part of the indication, REVOLADE may also be considered as second line treatment for adult non-splenectomised patients where surgery is contraindicated.

The efficacy and safety of REVOLADE in adult patients with chronic ITP were evaluated in three randomized, double-blind, placebo-controlled trials and in an open-label extension trial. Trial 1 randomized 114 patients (2:1) to REVOLADE 50 mg or placebo. Trial 2 randomized 117 patients (1:1:1:1) among placebo or one of three dose regimens of REVOLADE, 30 mg, 50 mg, or 75 mg each administered daily. In the third trial, 197 patients were randomized (2:1) to receive either REVOLADE 50 mg once daily

(n = 135) or placebo (n = 62) for 6 months, during which time the dose of REVOLADE could be adjusted based on individual platelet counts. Patients were allowed to taper or discontinue concomitant ITP medications after being treated with REVOLADE for 6 weeks. Overall, during clinical development for the ITP indication, REVOLADE showed a dose-dependent increase in platelet counts and a decrease in bleeding events compared with placebo, and was generally safe and well tolerated.

In addition to the ITP indication, the efficacy and safety of REVOLADE for the treatment of adult patients with chronic hepatitis C who were unable to initiate or maintain optimal interferon-based therapy due to thrombocytopenia were evaluated in 2 randomized, double-blind, placebo-controlled trials. The ENABLE 1 (Eltrombopag to INitiate and Maintain Interferon Antiviral Treatment to Benefit Subjects with Hepatitis C related Liver DiseasE) trial utilized peginterferon alfa-2a (Pegasys) plus ribavirin for antiviral treatment and ENABLE 2 utilized peginterferon alfa-2b (Pegintron) plus ribavirin. These global, randomized, double-blinded Phase 3 trials evaluated the efficacy of REVOLADE in 1521 HCV patients with platelet counts of less than 75×10^9 /L using a primary endpoint of achieving SVR and a secondary endpoint of early virologic response (EVR). In ENABLE 1, 66% of patients treated with REVOLADE plus Pegasys and ribavirin had an early virologic response, compared with 50% of patients who received Pegasys, ribavirin, and a placebo (p<0.0001). Additionally, 23% of the REVOLADE group achieved SVR versus 14% of the placebo group (p=0.0064) (Afdhal, 2012). In ENABLE 2, 62% of patients treated with REVOLADE plus Pegasys 2b and ribavirin had an early virologic response, compared with 41% of patients who received Pegasys, ribavirin, and a placebo (p<0.0001). Additionally, 19% of the REVOLADE group achieved SVR versus 13% of the placebo group (p=0.0202) (Dusheiko, 2012). REVOLADE was approved by the European Commission as a treatment for thrombocytopenia in adult patients with HCV, where the degree of thrombocytopenia is the main factor preventing the initiation or limiting the ability to maintain optimal interferon-based therapy in September 2013.

Regardless of indication, it is intended that REVOLADE dosing requirements be individualised based on the patient's platelet count, with the objective of treatment not to normalize platelet counts but rather to maintain platelet counts above a level that reduces the risk of bleeding (> 50 x 10⁹/L). The recommended starting dose for adults with chronic ITP is 50 mg once daily. For patients of East Asian ancestry, REVOLADE should be initiated at a reduced dose of 25 mg once daily. If after two to three weeks of therapy the platelet counts are below the clinically indicated levels (e.g., 50 x 10⁹/L), the dose may be increased by 25 mg to a maximum of 75 mg once daily. A treatment therapy cannot exceed a dose of 75 mg daily for patients with chronic ITP. The standard REVOLADE dose adjustment, either decrease or increase, would be 25 mg once daily. Patient platelet counts are to be monitored with dose adjustments made based upon platelet count response. For patients with chronic HCV associated thrombocytopenia, initial REVOLADE dose is 25 mg once daily. No dosage adjustment is necessary for

HCV patients of East Asian ancestry or patients with mild hepatic impairment. The dose of REVOLADE should be adjusted in 25 mg increments every 2 weeks as necessary to achieve the target platelet count required to initiate anti-viral therapy. Platelet counts should be monitored every week prior to starting antiviral therapy. A treatment therapy cannot exceed a dose of 100 mg REVOLADE once daily for patients with chronic HCV associated thrombocytopenia.

6.2. Rationale

ITP comprises a heterogeneous group of disorders and may occur in the absence of an evident predisposing etiology (called primary ITP) or secondary to a growing list of associated conditions such as chronic lymphocytic leukemia (CLL), Hodgkin's disease (HD), and non-Hodgkin's lymphomas (NHL) (called secondary ITP).

It is generally well-known that prescribing practices of any particular drug in real life clinical practice may differ from its use as defined in the authorized indications; therefore, this drug utilisation study (DUS) for REVOLADE will be conducted in several European countries to determine the indications for use and patient age ranges for which REVOLADE is currently being prescribed. This DUS will also explore patient characteristics in order to better understand the patient population receiving REVOLADE in routine clinical practice.

Databases containing health medical records or administrative medical claims can represent the most appropriate tool for drug use studies under some circumstances, due to the recording of diagnosis and prescription data generally performed either for administrative reasons or as part of the computerized management of patients records, independently of any study purposes, and due to the large panel of prescribers and associated population coverage. However, some key missing information such as platelet counts or relevant diagnoses will not be accurate enough or are only partially available in such databases or indirectly by means of proxy measures. In addition, REVOLADE may be prescribed by different specialists who must be accounted for while selecting a particular database. As a result, it was determined that a multi-national, multi-center retrospective medical chart review study was preferred to document REVOLADE utilisation patterns in real world practice. Based on IMS prescription sales data, France, Germany and Spain are the three highest REVOLADE using countries in Europe at this time. To gain a national perspective to the extent possible, approximately six or seven sites per country among these three will be selected and other countries as needed.

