8. RESEARCH METHODS

8.1. Study Design

This is a multi-national, multi-center study involving the retrospective review of approximately 300 to 450 patient medical records from selected European countries including France, Germany, Spain, and other relevant selected European Union (EU) Member States (see Section 8.2) with each country contributing approximately six or seven sites. It is estimated that 18 to 21 hospital or office based sites overall where prescribers of REVOLADE have been identified and medication records exist, will be targeted for recruitment. The investigators will be queried to identify REVOLADE treated patients during the periods of interest. To the extent possible, a selection of sites representative of the country prescription volumes will be enroled.

Medical records of all consecutive patients treated with REVOLADE, irrespective of indication, dose, treatment duration or any patient characteristic will be retrospectively reviewed to confirm eligibility.

Medical records will be reviewed for data from REVOLADE first prescription. This study involves no intervention, and will not impact the usual medical care or affect the treatment of patients. Thus, the study will reflect a real world medical practice without the potential for prescriber response bias, which may occur in prospective studies (i.e., the Hawthorne Effect) (Mangione-Smith, 2002).

The study overview is provided in the figure below:

[figure not shown]

Figure 1 REVIEU Study Overview

In Figure 1 EU approval for first indication (March 2010) refers to the approval of REVOLADE: "Revolade is indicated for adult chronic immune (idiopathic) thrombocytopenic purpura (ITP) splenectomised patients who are refractory to other treatments (e.g. corticosteroids, immunoglobulins). Revolade may be considered as

Page 116 WEUKBRE7133

second line treatment for adult non-splenectomised patients where surgery is contraindicated."

EU approval for second indication refers to "Revolade is indicated in adult patients with chronic HCV infection for the treatment of thrombocytopenia, where the degree of thrombocytopenia is the main factor preventing the initiation or limiting the ability to maintain optimal interferon-based therapy."

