8.3.2. REVOLADE General Information

The following data will be collected for all patients enrolled:

WEUKBRE7133

Page 120

• Date of informed consent.

The following data will be collected from the medical records for all patients enroled:

- Demographics:
 - o age at time of first REVOLADE prescribing dose
 - o gender
 - o race/ethnicity (where allowed by local regulation)
- Diagnosis of chronic ITP and date (if medical record data available, will record the disease phase as 'acute' or 'chronic' ITP specifically or just 'ITP', duration of ITP if available)
- Diagnosis of HCV and date; information on previous treatment with antiviral therapy
- Diagnosis of other conditions and date
 - o Hematologic malignancies (AML, MDS, other leukemia, lymphoma, etc)
 - o Aplastic anemia and bone marrow failure
 - o Other
- Medical history for applicable conditions and current medical conditions
 - Surgery (i.e., splenectomized or not)
 - Comorbidities that may be contraindications for surgery (anemia, hyperbilirubinemia, neutropenia, leukopenia, pancytopenia, pneumonia, and others)
 - o Pregnancy status
 - o Non haematological malignancy and type
 - o Comorbidities:
 - Cardiovascular diseases
 - Pulmonary Arterial Hypertension
 - Hypertension
 - Diabetes
- Treatment(s) preceding REVOLADE prescription:
 - Type (corticosteroids, immunoglobulins, cytokines, ribavirin, peginterferon, etc.)
 - Date of treatment initiation
 - Dose and duration
- Concomitant treatment(s) initiated with REVOLADE:
 - Type (corticosteroids, immunoglobulins, cytokines, ribavirin, peginterferon, etc.)
 - o Date of treatment initiation
 - Dose and duration
- All platelet counts (x10⁹/L) at the time of primary medical condition, at initiation of REVOLADE, and dates, and resulting in dose change, by dose

Page 121 WEUKBRE7133

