8.3.4. On label and off label definitions

If information on splenectomy, prior medication use, and contraindications for surgery is available, then use of eltrombopag for a patient will be categorized into the following groups:

- On-label use:
 - patient is an adult, has a diagnosis of chronic ITP, has been splenectomized or has a contraindication for surgery, and has received prior corticosteroids, immunoglobulins therapy; or
 - o patient is an adult, has a diagnosis of chronic HCV, has clinically meaningful thrombocytopenia limiting interferon-based therapy, and date of eltrombopag is after REVOLADE approval date (September 2013).
- Off-label use:
 - o patient is an adult, has chronic ITP, but has not received prior corticosteroids, immunoglobulins therapy or has not been splenectomized and does not have a contraindication for surgery;
 - o patient is an adult, has HCV, but does not have clinically meaningful thrombocytopenia limiting interferon-based therapy or the date of REVOLADE is prior to REVOLADE approval date;
 - o patient is an adult, but does not have ITP or HCV;
 - o patient is < 18 years of age

If there is no information on splenectomy, prior medication use, and contraindications for surgery, then classification will be more general:

- On-label use:
 - o patient is an adult and has a diagnosis of chronic ITP; or
 - o patient is an adult and has a diagnosis of HCV with clinically meaningful thrombocytopenia limiting interferon-based therapy, and date of eltrombopag after REVOLADE approval date
- Off-label use:
 - o patient is an adult, but has acute rather than chronic ITP;

- o patient is an adult, but does not have ITP and does not have HCV with clinically meaningful thrombocytopenia or has clinically meaningful thrombocytopenia limiting interferon-based therapy but date of eltrombopag is prior to REVOLADE approval date;
- o patient is an adult, but does not have ITP or HCV; or
- o patient is < 18 years of age

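### Secondary ITP can be counted as on-label: 8.3.4 asks only for chronic ITP and 8.3.2 records only its phase, although the protocol distinguishes primary from secondary ITP

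*Protocol*

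**What the plan says.** Section 6.2 of the protocol opens by splitting ITP into a primary form and one "secondary to a growing list of associated conditions such as chronic lymphocytic leukemia (CLL"), Hodgkin's disease and non-Hodgkin's lymphomas. Section 6.1 begins: "Chronic primary ITP is an acquired immune mediated disorder characterized by isolated thrombocytopenia", and the same sentence adds that there is no underlying cause. The Abstract says the same. The first EU indication is quoted in 8.1 as "Revolade is indicated for adult chronic immune (idiopathic) thrombocytopenic purpura (ITP) splenectomised patients", with further conditions.

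The classification itself is in 8.3.4, in two versions:

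- **Detailed rule**, used when splenectomy, prior medication and surgical contraindication are known. On-label means "patient is an adult, has a diagnosis of chronic ITP, has been splenectomized or has a contraindication for surgery", plus prior corticosteroid or immunoglobulin therapy.
- **Fallback rule**, used when that information is missing. On-label means "patient is an adult and has a diagnosis of chronic ITP".

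In both versions, adult use in other diseases is caught by the off-label bullet "patient is an adult, but does not have ITP or HCV". No bullet mentions secondary ITP.

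On data collection, 8.3.2 says that the site "will record the disease phase as 'acute' or 'chronic' ITP specifically or just 'ITP", with duration if available. It lists no item for type or cause of ITP. It does list other diagnoses with dates, including leukaemia and lymphoma, and 8.3.3 adds the indication for REVOLADE. Section 8.7.1 tabulates adults with chronic ITP and adults with cancer by type as separate rows. It neither crosses them nor makes them mutually exclusive.

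**The concern.** The study asks for which conditions the drug is prescribed (section 7) and whether prescribing follows the labelling (8.2.4). Thrombocytopenia attributed to another disease is one of the uses such a study should be able to show. The protocol draws the primary/secondary line in its background and then drops it at the two places where it would matter: the variable list and the label rule.

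Two consequences follow. First, the off-label proportion, which is the quantity used for the sample-size reasoning in 8.5.1, depends on a classification that the protocol leaves unstated. Second, the attribution of ITP to a cause is a judgement written in the chart. If it is not abstracted, it cannot be reliably rebuilt later from a list of co-existing diagnoses.

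**Working it through.** **Step 1. Run one patient through the rule.** Take an adult with chronic ITP recorded by the treating physician as secondary to lymphoma, using ITP in the 6.2 sense (primary or secondary).

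| Route in 8.3.4 | What it needs | Result |
|---|---|---|
| Detailed, on-label | adult, chronic ITP, splenectomy or surgical contraindication, prior therapy | on-label if all are met |
| Detailed, off-label ITP bullet | chronic ITP, but prior therapy or the surgical criterion not met | off-label, for a reason unrelated to the cause of the ITP |
| Fallback, on-label | adult, chronic ITP | on-label |
| Other-disease bullet, either rule | neither ITP nor HCV | does not apply |

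On this reading the secondary nature of the ITP never makes the patient off-label.

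If ITP in 8.3.4 is instead read in the 6.1 sense (primary only), the same patient has no ITP for the purposes of the rule and falls under the other-disease bullet as off-label. The two readings give opposite answers, and 8.3.4 does not choose between them.

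**Step 2. Reproduce the stated precision.** Inputs from 8.5.1: n = 400, p = 0.05, 95% confidence.

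Half-width = 1.96 × √(0.05 × 0.95 / 400) = 0.0214, giving 2.9% to 7.1%. This matches the protocol. All twelve cells of Table 1 reproduce in the same way to rounding; its column headed CI Width holds half-widths.

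**Step 3. Size of a reclassification.** Let s be the share of secondary ITP among patients the rule counts as on-label. The protocol gives no value, so s is an assumption shown over a range. The 5% is the protocol's own tentative off-label rate.

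Off-label proportion with secondary ITP moved = 0.05 + 0.95 × s

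| s (assumed) | Patients moved, n = 400 (380 × s) | Off-label proportion | 95% CI (same formula as Table 1) | Shift, points |
|---|---|---|---|---|
| 1% | 3.8 | 5.95% | 3.6% to 8.3% | 0.95 |
| 2% | 7.6 | 6.9% | 4.4% to 9.4% | 1.9 |
| 5% | 19 | 9.75% | 6.8% to 12.7% | 4.75 |
| 10% | 38 | 14.5% | 11.1% to 18.0% | 9.5 |

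**Step 4. Threshold.** The shift equals the half-width when 0.95 × s = 0.0214, so s is about 2.25%. In patients, 400 × 0.02136 = 8.5, or about 9 of 400. Below that share the shift is smaller than the stated precision; above it, larger.

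**The case against.** The strongest reply has four parts.

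*Nothing in the protocol places secondary ITP outside the label.* This is correct. A reader might infer from the word idiopathic in 8.1, read with 6.1, that secondary ITP is off-label and that the rule therefore understates off-label use. The documents do not support going that far: 6.2 describes the distinction in one sentence and does not build the study on it, and the indication as quoted names neither form. What stands is that the protocol must say how these patients are classified.

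*On-label status is not automatic.* Also correct. Under the detailed rule a patient with secondary ITP must still meet the surgical and prior-therapy criteria. Only the fallback accepts the chronic ITP diagnosis alone. It would be wrong to say that every adult with secondary ITP is counted as on-label.

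*The patients do not vanish.* Leukaemia, lymphoma, other diagnoses and the indication are collected, and 8.7.1 reports cancer and other diseases by type. Some secondary cases could be inferred from these. But 8.3.4 uses none of them to separate secondary ITP, a co-existing malignancy does not show that it caused the ITP, and 6.2 itself calls the list of causes a growing one. A statistical analysis plan could add a derivation rule. It could not supply an attribution that was never abstracted.

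*The size is assumed.* It is. At shares of 1% or 2% the shift stays within the stated 2.1 points, and a reader should not infer from the larger rows that the estimate is known to be badly off.

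**Conclusion.** The point holds as a gap in classification and data capture. The protocol distinguishes primary from secondary ITP, but neither the label rule nor the ITP item uses the distinction, so chronic secondary ITP can be counted as on-label. Whether that would be right or wrong against the authorised indication cannot be decided from this document.

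The effect on the off-label proportion depends wholly on an unknown share: 0.95 points at 1% and 9.5 points at 10%, starting from the tentative 5% rate. The more useful figure assumes no particular share: about 9 patients in 400 are enough to move the estimate by the full stated precision. The planned tabulation by condition is less exposed, although the link between ITP and its cause would not be visible there either. The change is worth making before abstraction starts, because the missing attribution is hard to recover afterwards.

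**What to change.** 1. Add one eCRF item to 8.3.2: *ITP type as documented: primary / secondary (state cause) / not documented*.
2. Reconcile 6.1, 6.2, 8.1 and 8.3.4 so that one defined term is used, and state in 8.3.4 how secondary ITP is classified against the authorised indication, in both the detailed and the fallback rule.
3. In 8.7.1, report adult secondary ITP as its own class and cross it with the cancer categories.
4. Report the off-label proportion twice, with secondary ITP counted as off-label and as on-label, so that the result does not hang on one reading of the label.

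The cost is one extra field, a short addition to 8.3.4 and an additional table. The type will be undocumented for some patients. Reporting that group separately shows how far the answer remains uncertain.
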